## **5.5 Study Evaluations**

Phone Screening:

Interested participants will complete a telephone screen with a research coordinator. Potential participants will be asked a variety of screening questions to determine eligibility. The phone

screening questions are included as an appendix 5. The screening includes the above inclusion/exclusion criteria and also includes questions about current physical activity and movement, the walking ability assessment and the six-item screener to determine if the participant has any cognitive impairment. The participant screening responses will be recorded directly into the study database located within the study folder on the J:drive (J:\MOTIVATE Walking (MIRB#01930) ).

## **2 Week Trial Period:**

After the subject has enrolled and has set up the Fitbit they will start a 2-week trial period. The participant will be instructed to wear the Fitbit Inspire the study team provided for them daily for two weeks and walk/move as they normally would. To sync the data the participant will need to open the application on their smart phone in close proximity to their Fitbit. The participant's step data is stored within their Fitbit accounts that will be accessed by the study team. The study team will record their available step-count data from the two-week trial period and use the procedures described above to establish a baseline average daily step count. . Research staff will only review the participant step data from days 7-13 for eligibility. Participants will not be aware of the dates we are reviewing for study inclusion.

If a participant walked less than 2,000/steps/day or more than 5,000 steps/day they will not be eligible for the study. Research study staff will call the participant and inform them if they are in the study or not. If there are fewer then 4 days of data reported days 7-13, we will extend the baseline window up to 2 weeks until 4 days of data can be established.

If a participant is not eligible, they will still be compensated for all study activities up to that point (consent visit, Fitbit visit and baseline survey). At this time participants will be able to keep their Fitbit.

The participants week 1 start date will start on their selected day of the week. If their baseline assessment period ends on a Monday and the participants chosen day of the week starts on a Saturday, then their week 1 wouldn't start until the following Saturday. This will be the same process regardless of the randomized group.

### **Data Syncing:**

To sync the data on most phones, the participant will need to open the application on their smart phone in close proximity to their Fitbit. The participant's step data is stored within their Fitbit accounts that will be accessed by the study team. The study team will record the participant's baseline step-count data in a study created Access database. Research staff will review the participant step data from days 0-7 to ensure it is being captured.

### **Surveys:**

The participants will need to complete a baseline survey (appendix 6) and follow-up surveys at weeks 12 and 24. The participants will be emailed/texted a link to complete the survey through Qualtrics. The participant will need to complete the baseline survey before finding out what group they are in. Under very rare circumstances if the participant is unable to complete the survey through Qualtrics we will offer the participant the opportunity to complete the survey over the phone with a research coordinator or completing a paper survey. Due to mailing issues, we will strongly encourage the phone survey option. The participant will receive the Qualtrics link after they have been consented and before the Fitbit visit. If the participant still has not completed the survey

by the Fitbit call, we will encourage the participant to complete the survey over the phone. If the participant completes the baseline survey through Qualtrics or over the phone, we will tell them what randomization group they are in and what that means for them. If the participant declines the survey over the phone, we will need their paper copy returned prior to starting the study. Once we receive the paper survey, we will call them to tell them what group they are in and their baseline week start date. They will be instructed to complete the mailed follow-up surveys as soon as possible during week 12 and 24 (appendix 6). The surveys will be completed either through the Qualtrics link or over the phone. Surveys collected over the phone will be recorded either in Excel or the study Access database in the study folder on the J:drive. Once mailed surveys are returned study staff will manually enter survey responses into either the Excel file or the Access database. Another study coordinator will cross check recorded responses to the paper surveys to ensure accuracy.

The survey is comprised of a variety of different measures that account for the secondary outcomes. The secondary outcomes are self-efficacy, intrinsic/extrinsic motivation and mental health.

Self-efficacy: Measured using the Exercise Self-Efficacy Scale at baseline, week 12 and week 24 (McAuley E 1993). This measure has respondents indicate how confident they are they could exercise five times per week at moderate intensity for thirty minutes or more given various conditions. This scale ranges from 0 (not confident) to 10 (very confident).

Intrinsic/extrinsic motivation: Measured using the Motivation for Physical Activity Measurement (MPAM) at baseline, week 12 and week 24 (Frederick CM 1993). This assessment measures the reasons and motivations for participating in physical activity. The assessment has the subject indicate why they exercise given various reasons and has the subject rate them on a scale 1 to 5. 1 indicates *it is very true for me* and 5 indicates *very untrue for me*.

Mental Health: Measured using the PHQ-8 depression scale at baseline, week 12 and week 24. The rating for this measure asks questions for how often during the past 2 weeks participants bothered by various events. The rating goes from not at all (0 on the scale), several days (1), more than half the days (2), nearly every day (3).

Additional measures that will be used include sociodemographics (from the VA survey of Health Experiences SHEP and Federal Reserve Board Survey of Household Economics and Decision Making), ENRICH Social Support Instrument (ESSI), Perceived Stress Scale, PROMIS sleep disturbance short form ((PHQ) and PROMIS Cooperative Group), Importance of Money Scale (IMS, Franzen and Mad), Loss Aversion (Gachter, Johnson and Herrmann), PROMIS Global Health Scale. These instruments are used to gather demographic data and how much social support and daily interaction the participant has with others. All of these assessments will be presented in the form of a cohesive survey, where responses are recorded based on a scale. Participants will select the response on the scale that most closely matches their life on the day they take the assessment.

Participants will be able to skip any survey responses that they prefer not to answer. All of the surveys are included in Appendix 6.

Main Study, weeks 1-24:

To participate, participants will be instructed to wear their Fitbits daily. Participants will need to open the Fitbit app on their phone and sync the Fitbit with the app on most phones. Participants will receive text message and/or emails with appropriate study updates. These updates will

include the new step goal for the next week, encouragement, reminders to sync the device with their phone, notification of non/financial incentives, lottery numbers, loss-framed results, reminders for surveys, transitioning into the maintenance phase, week 12-24 (appendix 22). All participants will select the day of the week when their new week starts. On the participants selected day, they will be given a new daily step goal for the next week.. The goal will be 15% more than the previous average weekly step count. If the participant is in a lottery group, they will participate in the lottery every day that they reach their new step goal. The text/email messages will be sent out the following day, i.e. "you won \_\_\_\_\_ in the lottery for your step count yesterday." For participants in the loss-framed group, the participants will get their update on points or dollar amount based on the previous day's steps.

Syncing:

Texts will encourage participants to sync their devices daily. If a participant fails to sync their Fitbit, they will continue to receive reminders to sync their Fitbit as soon as possible. Participants will receive text message reminders to sync their Fitbit or call us if they are having trouble. They will also get a reminder to charge their Fitbit if the charge drops below 15%. If a participant syncs sporadically, their step count will be adjusted to the most recent available data. In the absence of a full week of data, the average of the previous 7 days of data that was synced will be used.

Once the participant syncs their device (anytime week 1-12), they will get a text messages updating them on:

- 1) New daily step goal (the step goal will have been previously paused based on the most recent data we have. The next step goal will be based off whatever information is synced.)
- 2) All rewards won to date. Once a participant syncs their Fitbit, they will be sent a message with their lottery winnings or loss-framed point/dollar amount value based off what data was collected when the sync occurred.

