If someone is interested and passes the telephone screening, we will schedule a virtual enrollment visit (either phone, VA Video Connect or other approved video visit software such as WebEx, Teams, Zoom, etc.) Prior to the virtual visit, we will ask the participant if they are able and comfortable receiving the documents virtually. If they are, we will utilize DocuSign to send the consent and HIPAA authorization electronically. Using DocuSign, the participant will also get electronic copies of the documents once they have signed the documents. If they prefer hard copies, we will mail them an enrollment packet with two copies of all documents (Appendix 16). One copy they will keep for their records and the second they will return to us in the prepaid envelope. If the participant prefers, they will be able to use DocuSign to remotely sign the documents. We will also give them the option to sign the paper copies and email back a photo of their signature on the consent, and the last page of the HIPAA completely filled out.

If a participant is apprehensive about completing the consent visit and/or Fitbit set up visit virtually, and current local conditions allow for an in person visit, we will offer the Veteran an in person visit for the consent and Fitbit set-up (as one visit) or the Fitbit set-up. Each visit will have the same compensation as the virtual visit (\$25 each). For participants that complete both visits in person they will receive a link for the survey immediately following the visit. Participants must complete the survey by the end of the baseline period. Participants will not receive any additional compensation for completing the visit(s) in person and scheduling will be subject to local conditions and staff availability.

The enrollment packet will include the informed consent, HIPAA authorization, study overview, vendorization form and a postage paid envelope. The participant will go over the packet with a research coordinator. The coordinator will walk the participant through the informed consent and answer any questions they have. Once all of the participant's questions have been answered the participant will be instructed to return the signed copies through the pre-paid envelope or sign the electronic versions using DocuSign. Once the documents have been received by the research coordinator, the coordinator will immediately mail out the Fitbit packet.

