The QR code, which can be scanned by their mobile phone's camera, will open a hyperlink to a fully anonymous Qualtrics survey where participants can enter their Study ID and indicate if they are interested or not.

If someone is interested and passes the telephone screening (appendix 5 & 12), we will schedule a virtual enrollment visit. Prior to the virtual visit, we will mail them an enrollment packet with two copies of all documents or send electronic copies through DocuSign. For the paper copies, one copy they will keep for their records and the second they will return to us in the prepaid envelope. The enrollment packet will include the informed consent form, HIPAA authorization, study overview and a postage paid envelope. The participant will have the option to complete the forms via DocuSign (electronic signature), or by signing the consent and completing the last page of the HIPAA authorization, taking a photo of their signatures and emailing it to the study email account.

If the participant completes the documents electronically, we will immediately send out the survey through Qualtrics.

If the participant completes paper copies, the survey will be sent through Qualtrics immediately upon the staff receiving the copies.

The coordinators will set up an enrollment visit approximately 1-2 weeks after the mailing of the enrollment packet/electronically signing the consent & HIPAA depending on the current speed of the mail handled by the United States Postal Service. The visit will follow the format in appendix 8. The format for the visit will either be telephone, VA Video Connect, Teams, WebEx, or Zoom, depending on whatever the Veteran prefers.

When the documents have been returned, the coordinator will immediately mail out the Fitbit packet and submit to VA Finance the request to mail the participant the \$25 payment for completing the enrollment or provide an electronic giftcard. Each time the participant is paid they receive direct deposit. The participant will then speak with a research coordinator once they receive the Fitbit and will be instructed on how to set up the Fitbit up with their device (appendix 21). All participants will need to download the Fitbit app. Instructions provided to the participants and are included with this submission. Participants will be encouraged to open the application daily to sync their Fitbit with the app.

Consent staff:

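### The survey procedure in 5.5 would let some participants learn their group before the baseline step week is complete, while 5.2 assigns groups only after the step screen; the plan should state one order

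*Combined protocol and SAP*

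**What the plan says.** **Survey and disclosure (5.3; 5.5, Surveys).** For electronic consent, "If the participant completes the documents electronically, we will immediately send out the survey through Qualtrics". Section 5.5 agrees on the timing: "The participant will receive the Qualtrics link after they have been consented and before the Fitbit visit". If the survey is still open "by the Fitbit call, we will encourage the participant to complete the survey over the phone". Completion then triggers disclosure: "If the participant completes the baseline survey through Qualtrics or over the phone, we will tell them what randomization group they are in". If the participant returns a paper survey instead, "we will call them to tell them what group they are in and their baseline week start date".

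**Step screen (5.2; 5.5, 2 Week Trial Period).** "After the subject has enrolled and has set up the Fitbit they will start a 2-week trial period". Days 7-13 supply the baseline average and decide eligibility (2,000 to 5,000 steps/day). The review dates are kept from participants. Afterwards, "Research study staff will call the participant and inform them if they are in the study or not". Neither this call nor the matching one in 5.2 is said to disclose the group.

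**Assignment (5.1, 5.2).** Section 5.2 places assignment later, and says so twice. People who cannot install the app leave before they are assigned, and of up to 200 enrolled, 72 are expected to leave before assignment. Section 5.1 describes the randomisation but gives it no time.

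**Latest survey date.** In its paragraph on in-person visits, 5.2 says: "Participants must complete the survey by the end of the baseline period". Section 5.7 (Passive withdraw) allows 6 weeks from the Fitbit set-up visit.

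**The concern.** The two procedures cannot both be followed as written. Under 5.2 no group exists until the step screen is passed. Under 5.5 a finished survey is enough for staff to name the group, and the survey is meant to be finished by about the time the Fitbit is set up.

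The week in question does three jobs. It decides who enters the trial, it sets the first step goal, and it is the starting point of the primary outcome (Aim 1: change from baseline to week 24). A participant who knows the reward type has a motive to walk less in that week, because a low baseline makes the first goal easier. The news might equally prompt more walking. If the reaction differs between levels of a factor, most plausibly cash against non-financial or lottery against loss, then baseline steps, step-screen exclusions and change scores could differ by level with no true effect. Hiding the review dates shows that the protocol already wants this week undisturbed.

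**Working it through.** **1. The plan's own count.** From 5.2: 200 − 72 = 128. From Table 2: 16 × 8 = 128. The figure reproduces, and it describes assignment after the screen.

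**2. The literal 5.5 sequence, with Fitbit set-up as day 0.**

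| Event | Day | Source |
|---|---|---|
| Survey link sent | before 0 | 5.3, 5.5 |
| Survey urged by phone if still open | about 0 | 5.5 |
| Group told | on survey completion | 5.5 |
| Steps used for baseline and eligibility | 7 to 13 (window may be extended) | 5.2, 5.5 |
| Latest survey, 5.2 | end of baseline period | 5.2 |
| Latest survey, 5.7 | 6 × 7 = 42 | 5.7 |

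A survey finished before day 7 allows disclosure before the baseline week. One finished on days 7-13 allows it within that week, and one finished later is harmless. So 5.5, read literally, permits early disclosure for some participants. The documents do not say how many.

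**3. What any differential reaction would do.** No source gives a size, so this is a scale and not an estimate. Let *d* be the difference between two factor levels in how far knowing the group shifts baseline-week steps/day, averaged over everyone in the level, including those not told early.

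- Error in the change-score contrast, before the step window is applied: −*d*.
- Error after adjustment for baseline with slope *b*: −*b* × *d*. I assume *b* = 0.8, equal to the intra-class correlation in 5.6.
- Reference: the 375 steps/day in 5.6.

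| *d* (assumed) | Change score | Share of 375 | Adjusted | Share of 375 |
|---|---|---|---|---|
| 0 | 0 | 0% | 0 | 0% |
| 100 | 100 | 27% | 0.8 × 100 = 80 | 21% |
| 200 | 200 | 53% | 0.8 × 200 = 160 | 43% |

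The table shows absolute values; the sign reverses with the direction of the reaction. The week 1 goal would move by 1.15 × *d*, that is 115 or 230 steps/day.

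**4. With the 2,000 to 5,000 window applied.** A simulation used SD 2,300, correlation 0.8, a true effect of 375, and an assumed population mean of 5,000 or 6,500. Baseline steps were raised by *d* = 200 in one level. The change-score estimate was 208 to 211 and the adjusted estimate 213 to 215. The share passing the screen was 38.3% against 40.4% (mean 5,000), or 20.9% against 23.2% (mean 6,500). With *d* = 0 the estimates were 376 and 371, which is the true value up to simulation error.

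**The case against.** The best defence is that 5.5 sets a gate and not a time. The Surveys paragraph first says that the survey must be done before the group is learned. Read with 5.2, staff cannot disclose a group that does not yet exist. The message table in 4.0 fits this reading: survey reminders belong to the baseline period, and group-specific messages to the participant's weekly day.

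The paper route is also weaker evidence than it looks. Paper is the fallback when the phone survey is declined at the Fitbit call, so it would often come back during or after the trial period. *Baseline week* may then be loose wording for the start of the study. The term is used unevenly anyway: 5.6 equates it with the first week, while 5.2 discards the first week. The flowchart and Appendix 49 are not in the documents and may settle the order.

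A differential reaction is far from certain. Everyone is offered incentives, and the stated weekly values of lottery and loss are close ($14.20 and $14). The postcard mailings and the advice letter start in week 13. Walking below 2,000 risks exclusion, and the review dates are hidden. Under the weekly goal rule in 5.1 and 5.5, a shifted baseline acts directly on the week 1 goal only.

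All of this stands, and it limits what can be claimed. It does not supply the missing instruction to hold the group back.

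Three stronger readings are tempting and not supported:

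- **Early disclosure is what the plan intends.** Section 5.2 says otherwise, and late surveys cannot cause it.
- **All 72 exclusions (72/200 = 36%) would follow disclosure.** That needs every one of them to have finished the survey and been told first. Sections 5.2 and 5.7 also remove people for app or sync failure.
- **The order endangers the 8 per cell or the power.** No blocking is described, and the planned comparisons are main effects at 64 per level. Even an assumed split of 69 against 59 raises the standard error by only 0.3%: √[(1/69 + 1/59) / (2/64)] = 1.003.

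**Conclusion.** The conflict is real and worth fixing. Section 5.5 ties disclosure to survey completion alone, 5.2 puts assignment after app set-up and the step screen, and nothing in the documents tells staff which governs. The 5.2 order is probably intended. Followed literally, 5.5 would let some participants learn their group before or during days 7-13.

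The harm is possible but not established. It requires that some people are told early and that factor levels then react differently. The documents give neither quantity, so the bias has unknown size and direction and may be zero. The figures per 100 steps/day only show that a modest differential reaction would not be trivial beside 375. The planned sample size does not change.

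**What to change.** In 5.2 and 5.5, state: *Participants are randomised, and told their group, only after the baseline survey is complete and the baseline step count has been recorded and meets the 2,000-5,000 rule. Staff disclose the group in the call that tells participants they are in the study, or on survey completion if that is later.*

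In 5.5 (Surveys), take the group out of the survey-completion step on the Qualtrics, phone and paper routes. Change *baseline week start date* to *week 1 start date* and give it in the post-screen call. If the flowchart or Appendix 49 already states this order, align 5.5 with it.

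Record the dates of randomisation and disclosure. If anyone was told before their baseline week ended, report baseline steps and step-screen exclusions by factor level. I would not add a re-analysis that leaves those people out: they would be selected by how promptly they answered the survey, and could be much of the sample.

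Cost: disclosure moves to an existing call, with two date fields and, if needed, one descriptive table. No extra participants, visits or measurements.

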## 5.6 Data Analysis

There are 16 combinations of factors, with 8 patients in each, for a modestly sized trial of 128 patients. However, each factor has 64 patients per factor level: there are 64 people receiving financial and non-financial incentives for meeting PA goals, respectively, and 64 patients receiving them in the form of a lottery and a loss-framed incentive. Every component is balanced with respect to the other components, which allows us to estimate the effects of all components with nearly the same power as if we had conducted independent trials of each component.

We powered the analysis for a difference in steps between treatment groups at follow-up using a repeated measures design with 24 follow-up measures per person (weeks 1-24). We used data on the standard deviation in step count from the 2006 NHANES and applied the formula for a truncated normal distribution to estimate the standard deviation among subjects with <5,000 steps at baseline. This yielded an estimated standard deviation of approximately 2,300. We assumed an intra-class correlation of 0.8 for the follow-up measures. We will enroll 128 patients, or 64 patients per treatment arm. This is similar in size to the treatment arms in studies described in Table 3 that compared active treatment groups (n=70). The slightly smaller sample size in the present study is justified by the higher type 1 error probability assumption. Loss to follow-up in the trials in Table 3 ranged from 4-7%. With 128 patients we will have 80% power to detect a difference as small as 375 steps per day with 10% loss to follow-up. We anticipate recruiting at least 10 participants per month.

All data will be collected by the VA research study team. The data collected during the first week, week 0, also referred to as the baseline week, will be used for all future step goals. The VA research team will monitor this period to ensure the participant is actually participating and syncing the data. If there is no data, the VA study team will call and encourage the participant to participate or help troubleshoot any issues.

